8.1.2. Medical/vaccination history

Obtain the participant's medical/vaccination history prior to the current study pregnancy follow-up by interviewing the participant/parent(s)/LAR(s) and/or review of the participant's medical records. Record any vaccinations received from one month prior to the current pregnancy. Record any pre-existing conditions, signs and/or symptoms present prior to the current pregnancy in the eCRF.

8.2. Immunogenicity assessments

Not applicable.

8.3. Safety assessments

Planned timepoints for all safety assessments are provided in the SoA (Section 1.3).

8.3.1. Safety monitoring and committee

Safety evaluations will include those performed by investigators, as well as those by a SRT composed of GSK RSV team members.

A SRT is in place for each GSK product. It comprises of a global cross-functional team responsible for the ongoing assessment of benefit-risk for a product. The SRT contribute to the continual assessment of incoming new efficacy and safety information.

If the SRT's decision(s) after a safety evaluation require(s) them to take some action (e.g., to suspend, modify, or continue the conduct of the study for all groups or for selected groups), the SRT Chair (or his/her representative) will notify the study **CSL**. The study **CSL** will be accountable for notifying investigators in writing of the SRT's decision(s).

An external case adjudication committee will provide an independent, objective, blinded review and judgement on cases of preterm births. The scope of review by this committee will be limited to only review of gestational age at birth (to determine status of preterm birth cases) and preterm birth cases but may be expanded at the discretion of the GSK clinical study team. The details of structure and scope of this committee will be included in external case adjudication committee charter.

8.4. MAEs, serious adverse events (SAEs) and SAEs due to study participation, AESIs, and other safety reporting

For definitions relating to safety information see Section 10.2.

The investigator and any qualified designees are responsible for detecting, documenting, and recording events that meet the definition of a MAE, SAEs, AESI (see Section 10.2), SAE due to study participation and other safety information and remain responsible for following up all MAEs, SAEs, AESIs, SAEs considered related to the study participation that caused the participant to discontinue the study (see Section 7). This includes events reported by the participant (or, when appropriate, by a caregiver, surrogate, or the participant's legally authorized representative).

SAEs due to study participation, defined as SAEs which in the opinion of the investigator are related to the study participation (e.g., accident during any of the study contact and/or **study** visit) will be recorded throughout the study period.

The method of recording, evaluating, and assessing causality of SAEs and SAEs due to study participation and the procedures for completing and transmitting SAE due to study participation reports are provided in Section 10.2 and/or Section 8.4.6.

8.4.1. Time period and frequency for collecting MAE, SAE, and other safety information

All SAEs due to study participation will be collected from the signing of the ICF and/or IAF until Day 42 post-delivery or study conclusion at the time points specified in the SoA (Section 1.3).

SAEs assessed as related to study participation (e.g., protocol-mandated procedures) or related to a GSK product (non-IMP) will be recorded from the time a participant consents to participate in the study.

MAEs and SAEs for maternal participants will be collected during pregnancy until Day 42 post-delivery at the time points specified in the SoA (Section 1.3).

Table 6 Collection and reporting of safety information

Event	Visit 1 D1	Bi-annual contacts for 2 years until pregnancy	Initial Pregnancy Contact	Monthly contacts until Delivery	Delivery	Contact Day 42 post- delivery	Study Conclusion
SAEs related to study participation** or related to a GSK product							
Pregnancy outcome							
MAEs							
SAEs							
Pregnancy related AESIs							
Infant AESIs							
Infant MAEs							
Infant SAEs							

* i.e., consent obtained; D: Day, M: Month

** Any SAEs assessed as related to study participation (e.g., protocol-mandated procedures) or related to a GSK product will be recorded from the time a participant consents to participate in the study.

The shaded regions in the table indicate time period of data collection

All SAEs, AESIs and SAEs related to study participation will be recorded and reported to the sponsor or designee immediately and under no circumstance should this exceed 24 hours, as indicated in Section 10.2. The investigator will submit any updated SAE data to the sponsor within 24 hours of it being available and/or awareness.

A poststudy SAE is defined as any event that occurs outside of the SAE reporting period defined in Section 8.4.1 and Table 6.

Investigators are not obligated to actively seek information on SAEs after conclusion of the study participation. *However, if the investigator learns of any SAE, including a death, after a participant has been discharged from the study, the investigator must record it in the medical records. If the investigator considers the event to be reasonably related to study participation, the investigator must promptly notify the sponsor.*

8.4.2. Method of detecting SAEs and SAEs due to study participation

Care will be taken not to introduce bias when detecting SAEs and SAEs due to study participation. Open-ended and nonleading verbal questioning of the participant/participants' parent(s)/LAR(s) is the preferred method to inquire about SAEs and SAEs due to study participation occurrences.

8.4.3. Follow-up of SAEs and SAEs due to study participation

After the initial SAE report, the investigator is required to proactively follow each participant at subsequent visits/contacts. All SAEs and SAEs due to study participation will be followed until resolution, stabilization, the event is otherwise explained, or the participant is lost to follow-up (as defined in Section 7.3). Further information on follow-up procedures is provided in Section 10.2.3.5.

8.4.4. Adverse events of special interest

All pregnancy related AESIs will be collected during pregnancy until Day 42 post-delivery at the time points specified in the SoA (Section 1.3).

Infant AESIs will be collected from birth until Day 42 post-delivery at the time points specified in the SoA (Section 1.3).

8.4.5. Data Source and Data Collection for AESIs

8.4.5.1. List of AESIs

Pregnancy-related AESIs	Infant AESIs

 Hypertensive disorders of pregnancy: 
 gestational hypertension, pre-eclampsia, pre-eclampsia with severe features including eclampsia; Fetal growth restriction; Pathways to preterm birth: 
 premature preterm rupture of membranes, preterm labor, insufficient cervix provider-initiated preterm birth; Gestational diabetes mellitus; and Chorioamnionitis. 	
 Small for gestational age, Low birth weight including very low and extremely low birth weight (<2500 g, <1500 g, <1000 g), Congenital anomalies: 
 major external structural defects, internal structural defects, functional defects, Neonatal death 
 in a non-viable live birth [<22 weeks gestation] in an extremely pre-term birth [22.GA<28 weeks],

Pregnancy-related AESIs	Infant AESIs
	
 ○ in a preterm live birth [28.GA<37 weeks], ○ in a term live birth, ● Preterm birth

8.4.5.2. Retrospective data source and data collection

For *pregnancies completed (through Day 42 post-delivery) prior to enrollment*, medical data related to pregnancy outcome, pregnancy related AESIs and infant AESIs of any pregnancy conceived post-RSVPreF3 or control vaccination, based on medical records, will be retrospectively collected. ***Data collection will be done through a single structured participant contact to retrospectively collect information about any healthcare received by the mother and infant during pregnancy up to Day 42 post-delivery. This will identify the medical records for review, so that information about any outcome, medically attended event, SAE, or event of special interest is obtained directly from medical records.***

All relevant data collected in the medical records will be recorded in an electronic case report form (eCRF).

8.4.5.3. Prospective data source and data collection

For participants in the prospective cohort, prospective data collection related to pregnancy outcome, pregnancy related AESIs and infant AESIs of any pregnancy conceived post-vaccination ***and ongoing at enrollment or conceived after enrollment*** will be done through ***multiple structured participant follow-up contacts*** to collect information about any healthcare received ***by the mother and infant during pregnancy up to Day 42 post-delivery. This will identify the medical records for review, so that information about any outcome, medically attended event, SAE or event of special interest is obtained directly from medical records.***

- Follow-up contact every six months if not pregnant, up to 2 years (+2 months) post-vaccination/control.
- A follow-up Contact or Visit at the start of the pregnancy.
- Spontaneous reporting of pregnancy by study participants.
- Monthly contacts during any pregnancies conceived within 2 years post-vaccination/control, until Day 42 post-delivery.
- Follow-up Contact at Delivery.
- Follow-up Contact at Day 42 (~6 weeks) post-delivery.

All relevant data collected in the medical records will be recorded in an electronic case report form (eCRF).

8.4.6. Regulatory reporting requirements for SAEs, SAEs due to study participation and AESIs

- Prompt notification by the investigator to the sponsor of an SAE, SAE due to study participation and AESI is essential so that legal obligations and ethical responsibilities toward the safety of participants and the safety of a study intervention under clinical investigation are met. See Section 8.4.1 for reporting timeframes.
- For SAEs, SAEs due to study participation and AESI, the investigator must always provide an assessment of causality at the time of the initial report, as defined in the Section 10.2.3.3.
- An investigator who receives an investigator safety report describing an SAE due to study participation or other specific safety information (e.g., summary or listing of SAEs) from the sponsor will review and then file it along with the IB and will notify the IRB/IEC, if appropriate according to local requirements.

Table 7 Timeframes for submitting SAE due to study participation and other events reports to GSK

Type of event	Initial reports		Follow-up of relevant information on a previous report	
	Timeframe	Documents	Timeframe	Documents
SAEs	24 hours*†	Electronic Adverse Events Report	24 hours*	[paper/electronic] Adverse Events Report
SAEs due to study participation	24 hours*†	Electronic Adverse Events Report	24 hours*	[paper/electronic] Adverse Events Report
AESIs	24 hours*†	Electronic Adverse Events Report	24 hours*	[paper/electronic] Adverse Events Report

* Timeframe allowed after receipt or awareness of the information by the investigator/site staff.

† Paper Adverse Events Report will be dated and signed by the investigator (or designee). For each SAE due to study participation, the investigator(s) must document in the medical notes that they have reviewed the SAE due to study participation and have provided an assessment of causality

8.4.7. Contact information for reporting SAEs, SAEs due to study participation and AESIs**Table 8 Contact information for reporting SAEs, SAEs due to study participation and AESIs**

Study contact for questions regarding SAEs, SAEs due to study participation and AESIs Contact GSK's local and/or medical contacts
Contacts for reporting SAEs due to study participation Available 24/24 hours and 7/7 days [contact]

8.4.8. Additional reporting guidance for pregnancies reported during study period**8.4.8.1. Labor and Delivery**

- An *uncomplicated* vaginal delivery or planned cesarean section *expected* to occur in a hospital setting should NOT be reported as an AE, MAE or SAE.
- A medical *complication* that requires a cesarean section or an emergency induction may be reported as an SAE/AESI (as applicable), using the corresponding Expedited AE report form.

8.4.8.2. Reporting of congenital anomalies in relation to pregnancy outcomes and SAEs and/or AESIs

Table 9 summarizes the requirements for AESI/SAE reporting of adverse pregnancy outcomes when congenital anomalies are/are not present.

Table 9 Reporting pregnancy outcomes with or without congenital anomalies as AESIs and/or SAEs

	Live birth		Fetal death /stillbirth		Elective / Therapeutic Termination	
	AESI	SAE	AESI	SAE	AESI	SAE
None	-	-	-	X	-	X
Major ¹	X	if reportable per MACDP ³	-	X	-	X
Minor ²	-	if reportable per MACDP ³	-	X	-	X

* In the event of infant's participation in the study, congenital anomalies are to be reported in the infant's eCRF.

However, when there is no live birth, or no signed informed consent for the infant or the congenital anomaly is being reported for a subsequent pregnancy, it will be encoded in the maternal participant's eCRF.

¹Structural or functional defects that require surgical and/or medical treatment and that have serious adverse effects on health or development (functional) or have significant cosmetic impact.

²Anatomic variants or defects that do not have serious medical, functional or cosmetic consequences for the child.

³Metropolitan Atlanta Congenital Defects Program (MACDP) 6-Digit Code Defect List

Additional guidance when congenital anomalies are present are as follows:

The term “congenital anomaly” is broad. GSK uses the case definitions provided in the Centers for Disease Control and Prevention (CDC) Metropolitan Atlanta Congenital Defects Program guidelines, with specific reference to the MACDP 6-Digit Code Defect List [MACDP, 2021] to ensure that the collection and recording of these data is complete and consistent across studies and projects.

To report a pregnancy outcome of live birth with congenital anomaly as an SAE per these guidelines, an infant must have a birth defect that is *included in MACDP surveillance data* per the MACDP 6-Digit Code Defect List. (Congenital anomalies that are not included in MACDP surveillance data may be reported as medically attended or serious adverse events, if appropriate).

The characterization of major and minor congenital anomalies will follow CDC definitions [CDC, 2019]. Major congenital anomalies are structural or functional defects that require surgical and/or medical treatment and that have serious adverse effects on health or development (functional) or have significant cosmetic impact. They are always reported as AESIs, even if they are not reportable as SAEs.

Minor congenital anomalies are anatomic variants or defects that do not have serious medical, functional or cosmetic consequences for the child. Minor congenital anomalies are not to be reported as AESIs, even if they are reportable as SAEs.

If minor congenital anomalies are *not* reportable *as per MACDP*, they should be recorded on the infant *AE eCRF*. ***Whether the event was medically attended or not should also be recorded in the infant AE eCRF. If they are not medically attended, they should be reported in the infant AE eCRF as medically attended event category “none”.***

For example:

- Cleft palate is a major congenital anomaly and should be reported as an AESI. Per the MACDP 6 Digit Code Defect list, cleft palate is always included in MACDP surveillance data and should therefore also be reported as an SAE.
- If congenital aortic valve insufficiency or regurgitation meets the criteria for a major congenital anomaly, it is an AESI. Per the MACDP 6-digit code list, congenital aortic valve insufficiency or regurgitation is only included in MACDP surveillance data and should only be reported as an SAE if designated as moderate or severe, or (if the degree is not specified) if another heart defect is present. Other cases could be reported as medically attended or serious adverse events if the infant meets any other protocol criterion for a medically attended or serious AE because of the condition.
- Mongolian spots, in the absence of any associated findings represent a minor congenital anomaly. Per the MACDP 6-digit code list, they are never included in MACDP surveillance data. They are neither an AESI nor an SAE. They do not typically satisfy the criteria for a medically attended AE and so, in general, would only be recorded *on the infant AE eCRF*.

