4.5. Study limitations

- The study participants who decide to enroll in this study are already aware whether they received RSVPreF3 or control. Study participants from prior RSV MAT pregnancy studies who experienced an adverse pregnancy outcome or a pregnancy/infant event from a prior pregnancy, may choose to participate in the current study at different rates than those who did not. This may lead to selection bias. As we have information on prior vaccination/control and prior adverse events/outcomes, we can evaluate whether this occurs and consider statistical analysis approaches to adjust for this.
- Comparison between incidence of events or outcomes in this study and events or outcomes in previous RSV MAT studies likely cannot be made directly because of the following possible limitations: 1) the expected sample size for this study is too small for the study to be adequately powered for comparisons, 2) this study has different inclusion and exclusion criteria, 3) this study has different timepoint of pregnancy at enrollment (as early as possible), and 4) different risk factors for participants in this study, such as a relatively short inter-pregnancy interval for pregnancies included in this study.
- This study includes two cohorts, one for which ***all*** data will be collected retrospectively and the other cohort for which data will be collected prospectively (***with some retrospective data collection***). This approach was taken so that the number of enrolled participants can be maximized. However, this may result in underestimation of the true incidence of AESIs in a pooled cohort (retrospective and prospective), as the retrospective cohort is more subject to recall bias.
- This study is conducted with a proportion of the same participants enrolled in previous RSV MAT studies which uncovered a safety signal, as described in Section 2.2. As there is still no plausible mode of action or known imbalance in risk factors across RSVPreF3 vs. control groups identified that explains the safety signal, the possibility remains there is unknown confounding (an unmeasured risk factor or exposure) leading to the safety signal. If there is unknown confounding, that may lead to a similar safety finding in this study.

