10.2.2. Definition of SAE

An SAE is defined as any untoward medical occurrence that, at any dose, meets one or more of the criteria listed:	
a.	Results in death
b.	Is life-threatening The term 'life-threatening' in the definition of 'serious' refers to an event in which the participant was at risk of death at the time of the event. It does not refer to an event, which hypothetically might have caused death, if it were more severe.
c.	Requires inpatient hospitalization or prolongation of existing hospitalization 
 In general, hospitalization signifies that the participant has been admitted (usually involving at least an overnight stay) at the hospital or emergency ward for observation and/or treatment that would not have been appropriate in the physician's office or outpatient setting. Complications that occur during hospitalization are AE. If a complication prolongs hospitalization or fulfills any other serious criteria, the event is serious. When in doubt as to whether "hospitalization" occurred or was necessary, the AE should be considered serious. Hospitalization for elective treatment of a pre-existing condition that did not worsen from baseline is not considered an AE.
d.	Results in persistent or significant disability/incapacity 
 The term disability means a substantial disruption of a person's ability to conduct normal life functions. This definition is not intended to include experiences of relatively minor medical significance such as uncomplicated headache, nausea, vomiting, diarrhea, influenza, and accidental trauma (e.g., sprained ankle) that may interfere with or prevent everyday life functions but do not constitute a substantial disruption.
e.	Is a congenital anomaly/birth defect in the offspring of a study participant.
f.	Abnormal pregnancy outcomes (e.g., spontaneous abortion, fetal death, stillbirth, congenital anomalies*, ectopic pregnancy) *Refer to Section 8.4.8.2 for additional information.

10.2.3. Recording, assessment and follow-up of MAEs, SAE, SAE due to study participation and AESIs**10.2.3.1. SAE recording**

- When an SAE and/or SAE due to study participation occurs, it is the responsibility of the investigator to review all documentation (e.g., hospital progress notes, laboratory reports, and diagnostics reports) related to the event.

- The investigator will then record all relevant SAE and/or SAE due to study participation information.

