4.2.1. Definition of primary endpoints

The first pregnancy during study period is defined as the first pregnancy conceived post-vaccination or control in participants enrolled in RSV MAT studies (those previously received RSVPreF3 or control) up to Day 42 post-delivery.

Pregnancy outcomes include (not limited to):

1. Live birth
2. Spontaneous abortion

3. Stillbirth
4. Elective/therapeutic termination
5. Live birth Congenital anomaly(ies)
6. Spontaneous abortion Congenital anomaly(ies)
7. Fetal death/still birth Congenital anomaly(ies)
8. Elective/therapeutic termination Congenital anomaly(ies)

| Pregnancy-related AESIs | Infant AESIs |
|---|--|
| 
 • Hypertensive disorders of pregnancy: 
 – gestational hypertension, – pre-eclampsia, – pre-eclampsia with severe features including eclampsia; • Fetal growth restriction; • Pathways to preterm birth: 
 – premature preterm rupture of membranes, – preterm labor, – insufficient cervix – provider-initiated preterm birth; • Gestational diabetes mellitus; and • Chorioamnionitis. | 
 • Small for gestational age, • Low birth weight including very low and extremely low birth weight (<2500 g, <1500 g, <1000 g), • Congenital anomalies: 
 – major external structural defects, – internal structural defects, – functional defects, • Neonatal death 
 – in a non-viable live birth [<22 weeks gestation] – in an extremely pre-term birth [22.GA<28 weeks], – in a preterm live birth [28.GA<37 weeks], – in a term live birth, • Preterm birth |

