4.5.1. Adverse Events

Safety analyses in maternal participants will include summaries by study arms of MAEs, SAEs, SAEs due to study participation, and SAEs related to a GSK product.

Safety analyses in infant participants will include summaries by study arms and gestational age at birth (≥ 37 weeks; <37 weeks; overall) of MAEs, SAEs and SAEs due to study participation.

For MAEs until Day 42 post-delivery (Mothers: conception to Day 42 post-delivery; Infants: birth to Day 42), the number and percentage of maternal or infant participants with each MAE with exact 95% CIs will be tabulated by study arms and displayed by Medical Dictionary for Regulatory Activities (MedDRA) preferred term. By-participant listings will be prepared.

For SAEs and SAEs due to study participation, the number and percentage of participants with each SAE with exact 95% CIs will be tabulated by study arms and by MedDRA preferred term. By-participant listings will be prepared.

The number and percentage of maternal (or infant) participants and maternal pregnancies (based on pregnancies instead of subject) reporting

- at least one MAE
- at least one SAE
- at least one SAEs due to study participation

from study pregnancy conceived up to Day 42 post-delivery (or from delivery up to Day 42 post-delivery for infant participants) with exact 95% CIs will be tabulated by study arms.

A summary of number and percentage of participants with any recorded adverse events by maximum severity will be produced.

A separate summary will be provided for study intervention (administrated from previous RSV MAT studies) related MAEs and SAEs, respectively. A study intervention-related MAE (or SAE) is defined as a MAE (or SAE) for which the investigator classifies the possible relationship to study intervention from previous RSV MAT studies as “Yes”. A worst-case scenario approach will be taken to handle missing relatedness data, i.e. the summary table will include events with the relationship to study intervention as ‘Yes’ or missing.

Summaries of life-threatening and fatal SAEs by PT will also be created.

By participant listings of MAEs, SAEs and SAEs due to study participation will be prepared.

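### Elective and therapeutic terminations share one category and all count as SAEs, so no planned summary category isolates terminations for most medical reasons, and the pooled any-SAE comparison can be diluted or biased

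*Protocol*

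**What the plan says.** Protocol 8.4.8.2 introduces Table 9 as the table that "summarizes the requirements for AESI/SAE reporting of adverse pregnancy outcomes when congenital anomalies are/are not present". Its last pair of columns is headed "Elective / Therapeutic Termination". In all three rows (no anomaly, major anomaly, minor anomaly) the AESI cell is empty and the SAE cell is marked.

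Protocol 10.2.2 opens with "An SAE is defined as any untoward medical occurrence that, at any dose, meets one or more of the criteria listed". Criterion f adds "Abnormal pregnancy outcomes (e.g., spontaneous abortion, fetal death, stillbirth, congenital anomalies*, ectopic pregnancy". Termination of either kind is not among these examples.

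SAP 4.2.1 lists the pregnancy outcomes that form part of the primary endpoints. Row 4 is "Elective/therapeutic termination". Row 8 is the same merged category with congenital anomaly. The list is stated to be open-ended.

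SAP 4.5.1 says "For SAEs and SAEs due to study participation, the number and percentage of participants with each SAE with exact 95% CIs will be tabulated", and the sentence goes on to specify display by arm and by MedDRA preferred term. The same section plans a by-arm summary of participants, and of pregnancies, with any SAE. No exclusion for elective terminations is stated. SAP 6.3.2 gives similar any-SAE tables to the safety review team (Tables 24 and 25).

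Protocol 4.5 says "The study participants who decide to enroll in this study are already aware whether they received RSVPreF3 or control".

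**The concern.** A termination chosen for personal reasons is not a safety outcome. A termination because of maternal illness or a fetal problem may be one. The plan puts both in one outcome row and counts both as SAEs. Two things are at stake.

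First, row 4 of the outcome table belongs to a primary endpoint. A difference between arms in that row could not be interpreted from the table, because it might reflect choice, medical indication, or both.

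Second, the any-SAE percentage by arm takes in every voluntary termination. If these are equally frequent in both arms, they add the same kind of event to each and pull the ratio towards 1. If they differ because women know what they received, they create a difference with no medical cause. The study exists because of a pregnancy-related safety signal (Protocol 2.2), so a by-arm safety summary is likely to be read closely even though no hypothesis is tested.

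**Working it through.** **Step 1: the SAE rule.** Table 9 marks a termination with no anomaly as an SAE. Section 10.2.2 asks for an untoward medical occurrence. Two neighbouring rules exclude planned events: 8.4.8.1 keeps uncomplicated vaginal deliveries and planned cesarean sections out of AE, MAE and SAE reporting, and 10.2.2 does not treat hospitalization for elective treatment of an unworsened pre-existing condition as an AE. Table 9 takes a different line for elective termination and gives no reason.

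**Step 2: what the planned outputs can separate.**

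- Termination with a congenital anomaly: yes, SAP 4.2.1 row 8.
- Termination for a maternal medical reason: no summary category.
- Termination for a fetal reason without a recorded anomaly: no summary category.
- Elective termination: no summary category.
- Individual cases: visible in the participant listings of outcomes and SAEs (SAP 4.2, 4.5.1).
- Preferred-term tables: these set terminations apart from unrelated SAEs. The documents do not show whether the terms split elective from therapeutic.

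**Step 3: effect on the any-SAE summary.** The documents give neither a termination rate nor a maternal SAE rate, so there is no stated figure to reproduce and every rate below is an assumption. Let t be the proportion with an elective termination and b the proportion with some other SAE among the rest. Then

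P(any SAE) = t + (1 − t) × b = 1 − (1 − t)(1 − b).

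*Choice differs by arm (t = 5% versus 10%), no difference in b:*

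| Assumed b | Any SAE at t = 5% | Any SAE at t = 10% | Ratio |
|---|---|---|---|
| 10% | 1 − 0.95 × 0.90 = 14.5% | 1 − 0.90 × 0.90 = 19.0% | 1.31 |
| 15% | 1 − 0.95 × 0.85 = 19.25% | 1 − 0.90 × 0.85 = 23.5% | 1.22 |
| 20% | 1 − 0.95 × 0.80 = 24.0% | 1 − 0.90 × 0.80 = 28.0% | 1.17 |
| 30% | 1 − 0.95 × 0.70 = 33.5% | 1 − 0.90 × 0.70 = 37.0% | 1.10 |

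*Choice is the same in both arms, true ratio 1.5 in other SAEs (b = 15% versus 10%):*

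- t = 5%: 19.25% / 14.5% = 1.33
- t = 10%: 23.5% / 19.0% = 1.24
- t = 20%: 32.0% / 28.0% = 1.14

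With equal t and equal b the ratio is 1, so the classification alone creates no difference between arms.

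**The case against.** A reader might infer that terminations for medical reasons cannot be seen at all. The documents do not support that. Row 8 shows those with an anomaly, and the listings show each case. Because each termination is an SAE, it also brings 24-hour reporting, document review and a causality assessment, which makes single cases more visible. What stands is narrower: no summary category isolates a maternal reason, or a fetal reason without a recorded anomaly.

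A reader might also infer that Table 9 flatly contradicts 10.2.2. Criterion f is a list of examples, so absence from it is not exclusion, and Table 9 can be read as the specific rule for pregnancy outcomes. The opening requirement in 10.2.2 is still a fair reason to ask for reconciliation.

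A third inference would be that the study's main safety result follows personal choice. SAEs sit under other safety analyses (SAP 4.5). The primary endpoints are pregnancy outcomes and AESIs, Table 9 marks no termination as an AESI, and everything is descriptive. Only the pooled any-SAE summaries are exposed in this way.

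Arm-dependent choice is possible but not shown. Protocol 4.5 says that women know their allocation when they decide to enroll here. It does not say that they knew it when deciding about a pregnancy. Retrospective pregnancies were complete before enrollment, and the documents give no date of unblinding.

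Finally, removing elective terminations from SAE reporting has its own cost. SAE status would then depend on a judged reason, in a study where allocation is known, and that judgement could itself differ by arm. This objection stands, and it is why the fix below concerns summaries and leaves expedited reporting as it is.

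**Conclusion.** The point holds in limited form. The termination rule in Table 9 fits poorly with the definition in 10.2.2, and the two should be reconciled. The SAP merges a voluntary choice with a possible safety outcome in a primary-endpoint category, and it pools all terminations into any SAE by arm.

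The size is unknown. Under the assumed rates above, a twofold difference in elective termination gives a spurious ratio between 1.10 and 1.31, and equal termination rates of 5% to 20% shrink a true ratio of 1.5 to between 1.33 and 1.14. These figures show how the summary behaves and do not predict this study's results. The point does not undermine the AESI results. It is a cheap improvement that makes two by-arm summaries interpretable.

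**What to change.** 1. **SAP 4.2.1, rows 4 and 8:** split each into elective (no recorded maternal or fetal medical reason), therapeutic, and reason not recorded. Take the reason from the medical records already reviewed under Protocol 8.4.5.2 and 8.4.5.3.
2. **SAP 4.5.1, and SAP 6.3.2 Tables 24 and 25:** report any SAE by arm twice, with and without elective terminations without anomaly. Use the same denominator both times, so that the two rows differ only by these events.
3. **Protocol 8.4.8.2 and 10.2.2:** reconcile Table 9 with the SAE definition, or state why every termination is to be reported as an SAE. Expedited reporting stays as it is unless the sponsor changes it in that step.

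The cost is SAP wording, one extra row in the any-SAE summaries, and abstraction of the reason for termination. The eCRF is not among the documents, so that item may already be collected. The reason may be missing, or may be judged with allocation known, so the category for reason not recorded should be kept visible by arm.
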